### **8.5.2 Follow-up of AEs and SAEs**

Any AEs that are unresolved at the participant's last AE assessment in the study are followed up by the Investigator for as long as medically indicated, but without further recording in the eCRF. Fusion Pharmaceuticals retains the right to request additional information for any participant with ongoing AEs/SAEs at the end of the study, if judged necessary.

#### **AE variables**

The following variables will be collected for each AE;

- AE (verbatim)
- The date and time when the AE started and stopped (time is only required if the AE begins on a dosing day)
- CTCAE grade/changes in CTCAE grade
- Whether the AE is serious or not
- Investigator causality rating against the Investigational Product(s) (yes or no)
- Action taken with regard to Investigational Product(s)
- Outcome

In addition, the following variables will be collected for SAEs:

- Date AE met criteria for SAE
- Date Investigator became aware of SAE
- AE is serious due to
- Date of hospitalisation
- Date of discharge
- Probable cause of death
- Date of death
- Autopsy performed
- Causality assessment in relation to study procedure(s)
- Causality assessment to other medication

### **8.5.3 Causality Collection**

The Investigator should assess causal relationship between investigational product and each AE, and answer ‘yes’ or ‘no’ to the question ‘Do you consider that there is a reasonable possibility that the event may have been caused by the investigational product?’

For SAEs, causal relationship should also be assessed for other medication and study procedures. Note that for SAEs that could be associated with any study procedure the causal relationship is implied as ‘yes’.

A guide to the interpretation of the causality question is found in [Appendix B](#) to the CSP.

### **8.5.4 AEs Based on Signs and Symptoms**

All AEs spontaneously reported by the participant or reported in response to the open question from the study site staff: ‘Have you had any health problems since the previous visit/you were last asked?’, or revealed by observation will be collected and recorded in the eCRF. When collecting AEs, the recording of diagnoses is preferred (when possible) to recording a list of signs and symptoms. However, if a diagnosis is known and there are other signs or symptoms that are not generally part of the diagnosis, the diagnosis and each sign or symptom will be recorded separately.

### **8.5.5 AEs Based on Examinations and Tests**

The results from the CSP mandated laboratory tests and vital signs will be summarised in the CSR.

Deterioration as compared to baseline in CSP-mandated physical examinations, laboratory values, vital signs, and ECGs should therefore only be reported as AEs if they fulfil any of the SAE criteria, are the reason for discontinuation of treatment with the investigational product or are considered to be clinically relevant as judged by the Investigator (which may include but not limited to consideration as to whether treatment or non-planned visits were required or other action was taken with the study treatment, e.g., dose adjustment or drug interruption).

If deterioration in a laboratory value/vital sign is associated with clinical signs and symptoms, the sign or symptom will be reported as an AE and the associated laboratory result/vital sign will be considered as additional information. Wherever possible the reporting Investigator uses the clinical, rather than the laboratory term (e.g., anaemia versus low haemoglobin value). In the absence of clinical signs or symptoms, clinically relevant deteriorations in non-mandated parameters should be reported as AE(s).

Deterioration of a laboratory value, which is unequivocally due to disease progression, should not be reported as an AE/SAE.

Any new or aggravated clinically relevant abnormal medical finding at a physical examination as compared with the baseline assessment will be reported as an AE unless unequivocally related to the disease under study.

### 8.5.6 Hy's Law

Cases where a participant shows elevations in liver biochemistry may require further evaluation and occurrences of AST or ALT  $\geq 3 \times$  ULN together with total bilirubin  $\geq 2 \times$  ULN may need to be reported as SAEs. Please refer to [Appendix E](#) for further instruction on cases of increases in liver biochemistry and evaluation of Hy's Law.

Refer to the TMGs in Section [6.7.2](#) for management of participants with elevations in liver biochemistry.

### 8.5.7 Disease Progression

Disease progression can be considered as a worsening of a participant's condition attributable to the disease for which the investigational product is being studied. It may be an increase in the severity of the disease under study and/or increases in the symptoms of the disease. The development of new, or progression of existing metastasis to the primary cancer under study should be considered as disease progression and not an AE. Events, which are unequivocally due to disease progression, should not be reported as an AE during the study.

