### 8.5.8 Disease Under Study

Symptoms of disease under study are those which might be expected to occur as a direct result of participants' advanced solid tumour. Events which are unequivocally due to disease under study should not be reported as an AE during the study unless they meet SAE criteria or lead to discontinuation of the investigational product.

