### 8.5.9 Reporting of SAEs

All SAEs have to be reported, whether or not considered causally related to the investigational product, or to the study procedure(s). All SAEs will be recorded in the eCRF.

If any SAE occurs in the course of the study, then Investigators or other site personnel inform the appropriate Sponsor representatives within 1 day, i.e., immediately but **no later than 24 hours** of when he or she becomes aware of it.

The designated Sponsor representative works with the Investigator to ensure that all the necessary information is provided to the Sponsor's representative Patient Safety data entry site **within one calendar day** of initial receipt for fatal and life-threatening events **and within 5 calendar days** of initial receipt for all other SAEs.

For fatal or life-threatening AEs where important or relevant information is missing, active follow-up will be undertaken immediately. Investigators or other site personnel will inform Sponsor representatives of any follow-up information on a previously reported SAE within one calendar day, i.e., immediately but **no later than 24 hours** of when he or she becomes aware of it.

Once the Investigators or other site personnel indicate an AE is serious in the electronic data capture (EDC) system, an automated email alert is sent to the designated Sponsor

representative.

If the EDC system is not available, then the Investigator or other study site staff reports a SAE to the appropriate Sponsor representative by telephone.

The Sponsor representative will advise the Investigator/study site staff how to proceed.

The reference document for definition of expectedness for the IMPs in this study can be found in the IB.

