### **8.5.12 Deaths**

All deaths that occur during the study intervention period, or within the CSP-defined follow-up period after the administration of the last dose of study intervention, must be reported as follows:

- Death clearly resulting from disease progression should be reported to the Study Monitor/Physician at the next monitoring visit and should be documented in the eCRF. It should not be reported as an SAE.
- Where death is not due (or not clearly due) to progression of the disease under study, the AE causing the death must be reported as an SAE within 24 hours. It should also be documented in the eCRF. The report should contain a comment regarding the coinvolvement of PD, if appropriate, and should assign main and contributory causes of death.
- Death with an unknown cause should always be reported as an SAE. It should also be documented in the eCRF. A postmortem may be helpful in the assessment of the cause of death, and if performed, a copy of the postmortem results should be forwarded to Fusion Pharmaceuticals Patient Safety or its representative within the usual time frames.

As this study includes an endpoint of OS, deaths occurring after the CSP-defined safety follow-up period (28 or 42-days [+ 14 days]) after the administration of the last dose of study intervention should be documented in the eCRF. If the death occurred as a result of an event that started after the defined safety follow-up period and the event is considered to be due to a late-onset toxicity to study intervention, then it should also be reported as an SAE.

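### Sections 8.5.7 and 8.5.8 give conflicting reporting rules for non-fatal events unequivocally due to tumour worsening that are serious or lead to discontinuation

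*Protocol*

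**What the plan says.** Protocol section 8.5.7 describes disease progression as worsening attributable to the disease and adds: "It may be an increase in the severity of the disease under study and/or increases in the symptoms of the disease". Its reporting rule is: "Events, which are unequivocally due to disease progression, should not be reported as an AE during the study". It makes no exception for serious events or for events that end treatment.

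Section 8.5.8 has a different scope sentence, which refers to the participant's own tumour and begins: "Symptoms of disease under study are those which might be expected to occur as a direct result of". Its rule, where the tumour is unequivocally the cause, is that such events "should not be reported as an AE during the study unless they meet SAE criteria or lead to discontinuation of the investigational product".

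Three other places bear on the same events:

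- Section 8.5.9: "All SAEs have to be reported, whether or not considered causally related to the investigational product".
- Section 8.5.5, on laboratory values: "Deterioration of a laboratory value, which is unequivocally due to disease progression, should not be reported as an AE/SAE". The same section exempts examination findings that are unequivocally related to the disease under study.
- Section 8.5.12, on death clearly resulting from progression: "It should not be reported as an SAE".

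**The concern.** Participants have advanced tumours that have progressed on earlier treatment, so admissions for worsening tumour symptoms are foreseeable. The protocol should give a site one answer on whether such an admission is recorded. It gives two, and one of them carries the 24-hour SAE reporting duty of section 8.5.9.

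AE frequency, duration and severity are among the primary endpoints in section 3. Section 9.4.3 summarises SAEs separately if enough occur, and section 9.4.1 presents data by cohort and/or dose level. The Safety Review Committee reviews the safety data (section 6.7.8), and the RP2D draws on all available safety information (section 4.1). The study is multicentre and open-label without a control arm, so no comparator would show a difference in site practice. The analysis cannot restore events that sites were told not to record.

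**Working it through.** The check is mainly textual. The plan states no figure to reproduce.

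**Step 1: do the scopes overlap?** Section 8.5.7 includes increases in disease symptoms. Section 8.5.8 covers symptoms arising directly from the tumour and does not exclude symptoms that are getting worse. A worsening tumour symptom therefore fits both.

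**Step 2: apply each rule to each class of event.**

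| Event | 8.5.7 | 8.5.8 | Result |
|---|---|---|---|
| Unequivocal tumour worsening, not serious, no discontinuation | Not an AE | Not an AE | Agree |
| Unequivocal tumour worsening, non-fatal, meets SAE criteria (e.g. hospitalisation, Appendix B 2) | Not an AE | Reportable, as an SAE | Conflict |
| Unequivocal tumour worsening, not serious, leads to discontinuation | Not an AE | Reportable | Conflict |
| Tumour symptom without worsening, serious | Outside its scope | Reportable | No conflict |
| Death clearly due to progression | Not an AE | Would be reportable | Settled by 8.5.12: not an SAE |
| Cause in doubt | Not excluded | Not excluded | Agree |

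The conflict is confined to the second and third rows.

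**Step 3: does another passage settle those rows?**

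- Section 8.5.9 does not. Appendix B 2 defines an SAE as an AE that meets a seriousness criterion, so the duty to report all SAEs presupposes that the event is an AE. A site following 8.5.7 never reaches it.
- Section 8.5.12 settles deaths only.
- Section 8.5.5 covers laboratory values and examination findings. It points towards exclusion but does not address a symptomatic admission.
- No section states which of 8.5.7 and 8.5.8 takes precedence.

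**Step 4: size of one discrepant record.** A Part B dose level has 3 to 9 evaluable participants (section 4.1) and a backfill level about 20 (section 4.1.1). If one participant's only SAE is counted or not counted, the observed SAE proportion moves by 1/n:

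- n = 3: 1/3 = 33 percentage points
- n = 9: 1/9 = 11 percentage points
- n = 20: 1/20 = 5 percentage points

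The protocol gives no expected frequency of such events, so the sum over participants cannot be calculated.

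**Step 5: does it reach dose escalation?** Section 6.7.7 excludes from the DLT definition toxicities clearly related to disease progression. The suspension rule in section 6.7.4.1 makes the same exclusion. The mTPI-2 decisions (section 6.7.4) and the MTD (section 6.7.5) use DLTs, so they do not depend on which AE rule a site follows.

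**The case against.** The best defence is that the two sections have different objects: progression events are excluded, while disease symptoms short of progression are reportable when serious. Sections 8.5.5 and 8.5.12 lean the same way. So does Appendix B 2, whose instruction to treat malignant tumours as serious does not apply to progression of the tumour under study. This is a coherent reading, but the protocol does not state it. Section 8.5.7 brings increasing symptoms into progression, section 8.5.8 does not carve them out, and a site that applies the 8.5.8 exception is also following the text.

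Other parts of the defence stand and set the limits of the point:

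- A reader might infer that the exclusion hides toxicity mistaken for progression. Both sections exclude only events *unequivocally* due to disease, so a doubtful event is reportable under either. Misattribution by an unblinded investigator is possible, but the text does not show it.
- A reader might infer that Grade 3 or higher rates in general are distorted. A non-serious Grade 3 or higher event unequivocally due to disease that does not lead to discontinuation is excluded under both sections.
- A reader might multiply an assumed admission rate by the backfill size to obtain a number of affected participants. The protocol supplies no such rate. The product would also require every such admission to fall in the overlap, no affected participant to have another SAE, and a whole dose level to change rule together.
- AE summary tables count only events during treatment or the safety follow-up and before subsequent cancer therapy (section 9.4.3), which narrows the effect on those tables.

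**Conclusion.** This is an internal contradiction, wrong as written. It holds for non-fatal events unequivocally due to worsening of the tumour that meet SAE criteria or lead to discontinuation. For these, section 8.5.7 denies AE status, section 8.5.8 requires reporting, and nothing ranks the two.

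The consequence is inconsistent AE and SAE counts by dose level. One discrepant record is worth 33 points at n = 3, 11 points at n = 9 and 5 points at n = 20. These figures assume that the SAE denominator equals the number of evaluable participants and that the participant has no other SAE. The Safety Analysis Set also admits participants who received only the imaging agent, so a larger denominator would make the shift smaller. The total effect is unknown.

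A reader might take this as a threat to dose escalation. The documents do not support that, because progression-related events are already outside the DLT definition and the suspension rule.

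**What to change.** Reconcile sections 8.5.5, 8.5.7, 8.5.8 and 8.5.12 into one reporting rule for all sites. One way is to add to 8.5.7, and to the two disease-related sentences of 8.5.5, the exception that 8.5.8 already carries (SAE criteria met, or discontinuation of the investigational product). Section 8.5.12 would stay as the stated exception for deaths clearly due to progression. Changing 8.5.7 alone would not be enough, because 8.5.5 would then contradict it for serious laboratory deterioration due to progression.

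The opposite choice, limiting 8.5.8 to symptoms without worsening, would also remove the contradiction. The first option has the advantage that recorded events can be separated in the analysis, while unrecorded ones cannot be recovered.

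The cost is a clause in each affected section and somewhat more SAE reports for disease-related admissions. An eCRF flag for disease-attributed SAEs, with tables shown with and without them, would be useful but is optional.

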### 8.5.8 Disease Under Study

Symptoms of disease under study are those which might be expected to occur as a direct result of participants' advanced solid tumour. Events which are unequivocally due to disease under study should not be reported as an AE during the study unless they meet SAE criteria or lead to discontinuation of the investigational product.

### 8.5.9 Reporting of SAEs

All SAEs have to be reported, whether or not considered causally related to the investigational product, or to the study procedure(s). All SAEs will be recorded in the eCRF.

If any SAE occurs in the course of the study, then Investigators or other site personnel inform the appropriate Sponsor representatives within 1 day, i.e., immediately but **no later than 24 hours** of when he or she becomes aware of it.

The designated Sponsor representative works with the Investigator to ensure that all the necessary information is provided to the Sponsor's representative Patient Safety data entry site **within one calendar day** of initial receipt for fatal and life-threatening events **and within 5 calendar days** of initial receipt for all other SAEs.

For fatal or life-threatening AEs where important or relevant information is missing, active follow-up will be undertaken immediately. Investigators or other site personnel will inform Sponsor representatives of any follow-up information on a previously reported SAE within one calendar day, i.e., immediately but **no later than 24 hours** of when he or she becomes aware of it.

Once the Investigators or other site personnel indicate an AE is serious in the electronic data capture (EDC) system, an automated email alert is sent to the designated Sponsor

representative.

If the EDC system is not available, then the Investigator or other study site staff reports a SAE to the appropriate Sponsor representative by telephone.

The Sponsor representative will advise the Investigator/study site staff how to proceed.

The reference document for definition of expectedness for the IMPs in this study can be found in the IB.

### **8.5.10      Pregnancy**

All pregnancies and outcomes of pregnancy should be reported to the Sponsor's representative except for:

- If the pregnancy is discovered before the study participant has received any study intervention

#### **8.5.10.1    Maternal Exposure**

If a participant becomes pregnant during the course of the study, the investigational products should be discontinued immediately.

Pregnancy itself is not regarded as an AE unless there is a suspicion that the investigational product under study may have interfered with the effectiveness of a contraceptive medication. Congenital anomalies/birth defects and spontaneous miscarriages should be reported and handled as SAEs. Elective abortions without complications should not be handled as AEs. The outcome of all pregnancies (spontaneous miscarriage, elective termination, ectopic pregnancy, normal birth or congenital anomaly/birth defect) should be followed up and documented even if the participant was discontinued from the study.

If any pregnancy occurs in the course of the study, then the Investigator or other site personnel informs the appropriate Sponsor representatives within **1 day**, i.e., immediately but **no later than 24 hours** of when he or she becomes aware of it.

The designated Sponsor representative works with the Investigator to ensure that all relevant information is provided to the Sponsor's representative Patient Safety data entry site **within 1 or 5 calendar days** for SAEs (see Section [8.5.9](#)) and **within 30 days** for all other pregnancies.

The same timelines apply when outcome information is available.

The PREGREP module in the eCRF is used to report the pregnancy and the paper-based PREGOUT module is used to report the outcome of the pregnancy.

#### **8.5.10.2    Paternal Exposure**

Male participants should refrain from fathering a child or donating sperm during the study and 6 months following the last dose.

Pregnancy of the participant's partners is not considered to be an AE. However, the outcome

of all pregnancies (spontaneous miscarriage, elective termination, ectopic pregnancy, normal birth or congenital anomaly), occurring from the date of the first dose until 6 months after the last dose and as indicated by previous studies (nonclinical and clinical) should, if possible, be followed up and documented in the Pregnancy Report Form. Consent from the partner must be obtained before the Pregnancy Report Form is completed.

### **8.5.11 New Cancers**

The development of a new cancer should be regarded as an SAE. New primary cancers are those that are not the primary reason for the administration of the study intervention and have been identified after the participant's inclusion in this study. They do not include metastases of the original cancer.

### **8.5.12 Deaths**

All deaths that occur during the study intervention period, or within the CSP-defined follow-up period after the administration of the last dose of study intervention, must be reported as follows:

- Death clearly resulting from disease progression should be reported to the Study Monitor/Physician at the next monitoring visit and should be documented in the eCRF. It should not be reported as an SAE.
- Where death is not due (or not clearly due) to progression of the disease under study, the AE causing the death must be reported as an SAE within 24 hours. It should also be documented in the eCRF. The report should contain a comment regarding the coinvolvement of PD, if appropriate, and should assign main and contributory causes of death.
- Death with an unknown cause should always be reported as an SAE. It should also be documented in the eCRF. A postmortem may be helpful in the assessment of the cause of death, and if performed, a copy of the postmortem results should be forwarded to Fusion Pharmaceuticals Patient Safety or its representative within the usual time frames.

As this study includes an endpoint of OS, deaths occurring after the CSP-defined safety follow-up period (28 or 42-days [+ 14 days]) after the administration of the last dose of study intervention should be documented in the eCRF. If the death occurred as a result of an event that started after the defined safety follow-up period and the event is considered to be due to a late-onset toxicity to study intervention, then it should also be reported as an SAE.

### **8.5.13 Medication Error**

If a medication error occurs in the course of the study, then the Investigator or other site personnel informs the appropriate Sponsor representatives within **1 calendar day**, i.e., immediately but **no later than 24 hours** of when he or she becomes aware of it.

The designated Sponsor representative works with the Investigator to ensure that all relevant information is provided to the Fusion Pharmaceuticals Patient Safety data entry site within **1** (Initial Fatal/Life-Threatening or follow-up Fatal/Life-Threatening) **or 5** (other serious initial and follow-up) **calendar days** if there is an SAE associated with the medication error (see Section [8.5.9](#)) and **within 30 days** for all other medication errors.

For the purposes of this clinical study a medication error is an **unintended** failure or mistake in the treatment process for an IMP that either causes harm to the participant or has the potential to cause harm to the participant.

The full definition of a medication error can be found in Appendix [B 4](#).

